make recommendations to the Principal Investigator, and, if required, to the Food and Drug Administration (FDA) concerning continuation, termination or other modifications of the trial based on the observed beneficial or adverse effects of the treatment under study;

The DSMB will discharge itself from its duties when the study is complete.

Board Process

At each meeting, the DSMB will discuss the protocol, suggested modifications, and establish guidelines to study monitoring by the Board. The a designated DSMB Chairperson, in consultation with the Principal Investigator and study staff, will prepare the agenda to address the review of study materials, and the reporting of adverse events.

Meetings of the DSMB will take place quarterly, until the completion of the study. An emergency meeting of the DSMB may be called at any time should participant safety questions or other unanticipated problems arise.

Meetings shall be closed to the public because discussions may address confidential participant data. Meetings are attended by the Principal Investigator and members of his/her staff. Meetings may be convened as conference calls as well as in-person.

Meeting Format

DSMB meetings will consist of open and closed sessions. Discussion held in all sessions is confidential. The Principal Investigator and key members of the study team attend the open sessions.

Open session discussion will focus on the conduct and progress of the study, including participant accrual, protocol compliance, and problems encountered.

The closed session will be attended by the DSMB members.

Each meeting must include a recommendation to continue or to terminate the study made by a formal DSMB majority or unanimous vote. Should the DSMB decide to issue a termination recommendation, the full vote of the DSMB is required. In the event of a split vote, majority vote will rule, and a minority report should be appended. The DSMB Chair provides the tiebreaking vote in the event of a 50-50 split vote.

A recommendation to terminate the study may be made by the DSMB at any time by majority vote. In the event that the DSMB requires the study to be terminated, the PI will be immediately informed about their decision.

Meeting Materials

DSMB interim report templates will be prepared by the study staff, to be reviewed by the DSMB members at the first meeting. Interim data reports generally consist of two parts:

Part 1 - Open Session Report
Part 2 - Closed Session Report

Format and content of the reports for both the open and closed sessions and plans for interim analyses should be finalized and approved at the initial DSMB meeting, although changes throughout the trial may be requested by the Board.

The reports will list and summarize safety data and describe the status of the study. All meeting materials should be sent to the DSMB members at least 1 business day prior to the meeting.

Part 1 - Open Session Reports: Open session reports generally include administrative reports by site that describe participants screened, enrolled, completed, and discontinued, as well as baseline characteristics of the study population. Other general information on study status may also be presented. Listings of adverse events and serious adverse events as well as any other information requested by the DSMB may also be in the open session report, but none of the data should be presented in an unblinded manner. The DSMB may direct additions and other modifications to the reports on a one-time or continuing basis.

Part 2 – Closed Session Report: Closed session reports generally present the same information as presented in the open session but by blinded treatment group. The reports may also contain data on study outcomes, including safety data, and depending on the study, perhaps efficacy data. The Closed Session reports should be destroyed at the conclusion of the meeting. If the meetings are held by telephone, printed copies of the closed reports should be destroyed immediately following the meeting. If a study has an interim analysis, it is also discussed in the closed session.

Reports from the DSMB

A formal report containing the recommendations for continuation or modifications of the study will be prepared by the DSMB Chairperson. Once approved by the DSMB members, the DSMB Chair will forward the formal DSMB recommendation to the Principal Investigator, within 2 weeks of the DSMB meeting. It is the responsibility of the Principal Investigator to distribute the DSMB recommendation to all co-investigators and to ensure that copies are submitted to all the IRBs associated with the study.

Confidentiality

All materials, discussions and proceedings of the DSMB are completely confidential. Members and other participants in DSMB meetings are expected to maintain confidentiality.

B7-1 Study: Schedule of Events (SOE)

Study Visits	Screening	Day 1 60 days	Day 15 + 5 days	Day 29 M 1 + 5 days	Day 43 M 2 + 5 days	Day 57 M 3 + 5 days	Day 85 M 4 + 5 days	Day 113 M 5 + 5 days	Day 141 M 6 + 5 days	Day 169 M 7 + 5 days	Day 197 M 8 + 5 days	Day 225 M 9 + 5 days	Day 253 M 10 + 5 days	Day 281 M 11 + 5 days	Day 309 M 12 + 5 days	Day 337 M 13 + 5 days	M18 + 5 days	
Procedures																		
Full Medical History	X																	
Physical Exam	X																	
Vital Signs^a	X	X	X	X	X	X	X	X	X	X	X	X	X	X	X	X		
Chart Review Only																X	X ^f	
Serum or Urine Pregnancy Test (WOCBP only*)	X*																	
EBV Serology^a	X																	
Spot Urine Protein/ Creatinine Ratio^a	X			X			X			X			X			X		
Urine^{a,b}	X			X			X			X			X			X		
Cholesterol Panel^a	X															X		
Serum Glucose^a	X			X			X			X			X			X		
Serum Creatinine^a	X			X			X			X			X			X		
anti-HLA Antibody^c	X ^a															X		
B7-1 biopsy staining^c	X																	
Research Urine^c	X															X		
Research Blood^c	X															X		
Belatacept Infusions^a		X	X	X	X	X	X	X	X	X	X	X	X	X	X	X		
CNI Taper		X ^d	X ^d	X ^e														
AE/SAE Reporting		X	X	X	X	X	X	X	X	X	X	X	X	X	X	X		

KEY:

^aStandard of Care (SOC)

^bUrine = urinalysis w/sediment **AND** Spot Urine = Urine:Creatinine & Urine:Protein; **AND** Urine Protein/Creatinine ratio = calculation needed

^cCentral Lab = send to BWH (transplant research center, [name])

^dCNI dosing to be tapered 25% of baseline dose **PER WEEK** (weekly reduction NOT represented on this SOE), dates of reduction must be documented in eCRFs.

^eLast day of CNI; CNI completely stopped after this day.

^fCollect information about last blood pressure, medications, serum creatinine and urine protein/creatinine

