Secondary: Assess the effect of Belatacept conversion in the percent change of renal function from baseline to 12 months; donor-specific anti-HLA antibodies presence and intensity (MFI); correlation of B7-1 positivity on immunofluorescence on biopsy with B7-1-expression in urine extracellular vesicles; adverse events; acute rejection episodes; blood pressure control; new onset diabetes; hyperlipidemia; graft survival; and patient survival.

Study design:

Inclusion Criteria:

1. Male or female adult kidney transplant recipients older than 18 years old
2. eGFR $\geq 30\text{ ml/min}$
3. ≥ 6 months after transplantation
4. Proteinuria $\geq 1\text{ gram/day}$ in spot urine protein/creatinine ratio
5. Available biopsy specimen for B7-1 staining at recruitment time.
6. Ability to provide written informed consent for the study.
7. Maintenance immunosuppression of CNI (cyclosporine or tacrolimus), antiproliferative agent (azathioprine, MMF or MPA) with either steroids or not.
8. Must be EBV IgG positive

Exclusion Criteria:

1. Age < 18 years

2. eGFR<30 ml/min
3. active acute cellular rejection (ACR; higher than borderline) or ACR in the previous 6 months; active acute antibody-mediated rejection.
4. recurrent FSGS
5. EBV IgG negative
6. patient on mTOR inhibitor (e.g. Everolimus, Sirolimus)
7. patient only on CNI (cyclosporine or tacrolimus) and steroids

Accrual Goal: 36 subjects, 3 study sites

Accrual Rate: approximately 2 subjects/month; total of 18 months enrollment; 18 months of follow-up

First Patient First Visit: 1-March-2015

Statistics: This is a Phase I clinical trial to test the safety and gain further insight into the potential effect of Belatacept in proteinuric kidney transplant patients. We plan to recruit 36 patients, based on the feasibility for recruitment in 3 transplant centers and prior literature on recommended sample sizes in a Phase I trial.

2. Background:

Although improvements in immunosuppression have led to a reduction in acute rejection rates, long-term allograft survival remains disappointing, with more than 50% of allografts lost 10 years after transplantation.

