We propose to perform a multi-center study in which adult kidney transplant recipients with proteinuria (≥ 1 g/day) will be converted from CNI to Belatacept (**Figure 3**) once B7-1 staining has been performed on allograft biopsy ([name] will be performing all stains). This is a Phase I study that will aim to enroll 36 patients in 18-month recruitment time involving 3 transplant sites. Other inclusion criteria include: eGFR > 30 ml/min, greater than 6 months post-transplant and EBV IgG positive status. **Exclusion criteria** include: age < 18 years, eGFR < 30 ml/min, active acute cellular rejection (ACR; higher than borderline) or ACR in the previous 6 months, recurrent FSGS, EBV IgG negative status and on mTOR inhibitor as maintenance immunosuppression.

[figure not shown]

Figure 3. Study Design. Protocol and outcomes measures are detailed.

Patients that develop proteinuria after transplant are a heterogenous group with many potential

underlying etiologies including calcineurin inhibitor toxicity, transplant glomerulopathy, BK nephropathy or recurrent glomerular disease (4). Therefore, we decided to enroll 12 patients per center (3 centers total) to allow the inclusion of different etiologies of proteinuria and be a feasible study based on our inclusion criteria.

By including both B7-1 positive and B7-1 negative patients with proteinuria in the study, we will have the best chance of success and it would also allow for future testing for other potential prognostic markers in this population. One of the main reasoning's behind this is that the B7-1 staining is undergoing further optimization by [name] and a NIH task force, and therefore, restricting our recruitment may limit interpretation of the data in case the staining changes. This has been previously shown to be most productive approach in biomarker-driven interventions in the cancer field (11). In addition, the exact mechanism in which B7-1 targeting reduce proteinuria is still debated. By including both B7-1 positive and B7-1 negative patients with proteinuria, we will be able to assess overall risk factors and have a control group with no B7-1 staining treated with Belatacept. A historical control group with patients that fit the inclusion criteria and were managed as standard of care at our institution will also be included for comparison.

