The **primary endpoint** of the study will be a 25% reduction in proteinuria from baseline to 12 months. This endpoint was extrapolated from studies with ACE inhibitors showing significant benefit in patients with kidney disease and proteinuria that reached this endpoint (12). **Secondary end-points** include: percent change of renal function from baseline to 12 months; donor-specific anti-HLA antibodies presence and intensity (MFI); correlation of B7-1 positivity on immunofluorescence on biopsy with B7-1-expression in urine extracellular vesicles; adverse events; acute rejection episodes; blood pressure control; new onset diabetes; hyperlipidemia; graft survival; and patient survival. At 18 months, we will perform a chart review to check if patient remained or not on Belatacept, their renal function, proteinuria and biopsy-proven rejection events since trial termination.

Developing a **urinary biomarker to non-invasively detect patients with B7-1 expression on allografts** is another goal of this study. This will not only allow monitoring of treatment effectiveness and serving as secondary end-points but will also permit non-invasively screening for B7-1 positivity in patients in the future. Briefly, we will isolate RNA from urinary extracellular vesicles (EVs) of transplanted patients and detect B7-1 mRNA using "Droplet Digital" PCR system. EVs such as exosomes (40-100 nm in diameter) and microvesicles (100-1000 nm) are nanometer-sized vesicles released by cells including kidney podocytes to mediate cell-to-cell communication by delivering proteins and genetic materials such as mRNAs and microRNAs (13). We hypothesize that podocytes expressing B7-1 will shed EVs into the urine that will carry B7-1 mRNA. [name] laboratory at the Transplantation Research Center (Co-Investigator) optimized the isolation of high quality and quantity of RNA from urinary EVs of transplant patients (Figure 4).

Enrolled patients will have serum and urine collected at time of conversion and 12 months post-conversion. Urine will be processed for extracellular vesicles (EVs) and mRNA isolation. Samples will be stored at minus 80 degrees Celsius freezer until analysis. Future alternative approaches for characterization of B7-1 expression on kidney allografts involve determination of urinary B7-1 mRNA

[figure not shown]

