All study investigators and study staff must follow all appropriate requirements, including Good Clinical Practice (GCP), International Conference on Harmonization (ICH), Code of Federal Regulations (CFR), and the Partners Human Research Committee (PHRC) Institutional Review Board (IRB). The study will be conducted in compliance of the protocol. The protocol, all amendments, and the subject informed consent will receive Institutional Review Board/Independent Ethics Committee (IRB/IEC) approval/favorable opinion before initiation of the study. Study personnel must be qualified by education, training and experience to perform their respective tasks, and will not utilize personnel for whom sanctions have been invoked or where there has been scientific misconduct or fraud.

Appropriate study personnel will obtain signed and dated informed consent from each study participant. [Investigators will ensure that subjects, or their legally acceptable representatives, are clearly and fully informed about the purpose, potential risks, and other critical issues regarding this clinical research study in which they voluntarily participate. The approved consent form will adhere to the ethical principles that have their origin in the Declaration of Helsinki. All relevant safety information regarding the dose/schedule of study drug, or any other drugs/procedures in this clinical study must be explained in the informed consent document. Informed consent will also delineate which authorities may have direct access to study records and documents. Consent will also clearly state that although [name] is the study sponsor, Bristol-Myers Squibb (BMS) is the study funding source and is also supplying study drug for this study.

7. Eligibility:

7.1 Inclusion Criteria:

- Deceased or living donor adult kidney transplant recipients older than 18 years old
- eGFR >30 ml/min
- >6 months after transplantation
- Proteinuria >1 gram/day in spot urine protein/creatinine ratio
- Available biopsy specimen for B7-1 staining at recruitment time.
- Ability to provide written informed consent for the study.
- Must be EBV IgG positive

7.2 Exclusion Criteria:

- Age <18 years
- eGFR<30 ml/min
- Active acute cellular rejection (ACR; higher than borderline) or ACR in the previous 6 months; active acute antibody-mediated rejection.
- Recurrent FSGS
- EBV IgG negative

- Patient on mTOR inhibitor (e.g. Everolimus, Sirolimus)
- Age and Reproductive Status:

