The primary endpoint of the study will be a 25% reduction in proteinuria from baseline to 12 months. This endpoint was extrapolated from studies with ACE inhibitors showing significant benefit in patients with kidney disease and proteinuria that reached this endpoint (12). For comparison, we will also have a historical control group with patients that fit the inclusion criteria and were managed as standard of practice on our institution. A logistic regression model will be used to control for key variables such as baseline ACEI/ARB use, level of proteinuria, age and gender.

For the primary endpoint: Percentage of those patients who have a $\geq 25\%$ reduction in proteinuria from baseline to 12 months will be reported separately for each group. We will compare these percentages between the two groups using Fisher's exact test. In addition, means and standard deviations of the actual reduction will be reported separately for each group and will be compared between the two groups using a non-parametric test (Wilcoxon rank-sum). These results will also be compared to historical controls. A logistic regression model will be used to control for key variables such as baseline ACEI/ARB use, level of proteinuria, age and gender.

For the secondary endpoints: Descriptive statistics (means, standard deviations and/or percentages) will be reported on percent change of renal function from baseline to 12 months; donor-specific anti-HLA antibodies presence and intensity (MFI); adverse events; acute rejection episodes; blood pressure control; new onset diabetes; and hyperlipidemia. Spearman correlations will be calculated between B7-1 positivity on immunofluorescence on biopsy with B7-1-expression in urine extracellular vesicles. Kaplan-Meyer plots will be used to study graft survival and patient survival and a proportional hazards model will be used here to compare survival between treated and historical controls, controlling for the baseline covariates above.

References:

2. Halimi J-M. Low-grade proteinuria and microalbuminuria in renal transplantation. *Transplantation*. 2013;96(2):121-30.

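### The only scheduled pre-treatment UPCR is at Screening and no baseline sample is named; if the value that qualifies the patient is also the baseline, regression to the mean inflates the reported response

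*Combined protocol and SAP*

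**What the plan says.** Section 7.1 admits patients on "Proteinuria >1 gram/day in spot urine protein/creatinine ratio"; the synopsis uses the same criterion with a greater-or-equal sign. Neither asks for a repeat sample. Both also require "Available biopsy specimen for B7-1 staining at recruitment time".

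Section 11 defines the outcome: "The primary endpoint of the study will be a 25% reduction in proteinuria from baseline to 12 months". The percentage meeting it is given for each group and compared by Fisher's exact test. In addition, "means and standard deviations of the actual reduction will be reported separately for each group", and "These results will also be compared to historical controls". A logistic model adjusts for level of proteinuria, among other covariates.

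The Schedule of Events marks the row "Spot Urine Protein/ Creatinine Ratio" at Screening and Days 29, 85, 169, 253 and 337. The separate urinalysis row has the same pattern. Day 1, the first infusion, has neither.

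Section 6 adds: "Enrolled patients will have serum and urine collected at time of conversion and 12 months post-conversion". That urine is for extracellular-vesicle and mRNA work, and the Schedule places the research urine at Screening and Day 337. It is not a second UPCR.

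No visible text says which UPCR is the baseline, for trial patients or for historical controls.

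**The concern.** A single spot UPCR varies from sample to sample. Patients admitted because one reading reached 1 g/day include some whose reading happened to be high that day. If that reading is also the denominator of the percentage change, later readings will on average be lower even if nothing has changed.

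The quantities exposed are the response percentage and mean reduction reported for each group. The comparison with historical controls is exposed only if the two sides choose their baseline differently, and the plan states no rule for either.

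**Working it through.** The plan gives no response rate, UPCR variability or power, so there is no figure of its own to reproduce. What follows is a model with stated assumptions.

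**From the documents:** entry cut-off 1 g; response is a final value at or below 0.75 times baseline; 36 patients.

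**Assumed:** log-normal true levels; screened-pool median 0.5 to 2.5 g; between-patient log-SD (sb) 0.5 or 0.8; within-patient CV 20% to 50%, independent between visits; no true change.

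**Formulas.** Within-patient log-SD: sw = sqrt(ln(1 + CV²)). SD of one log reading: s1 = sqrt(sb² + sw²). Correlation of two readings: r = sb²/s1². Let L1 and L2 be the log Screening and final values.

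- Baseline independent of selection: P(response) = Φ(ln 0.75 / (sw·√2)).
- Screening value qualifies and is baseline: P(L2 − L1 ≤ ln 0.75 | L1 ≥ 0), by numerical integration.

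**Worked case: CV 40%, median 1.0 g, sb 0.5.**

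- sw = sqrt(ln 1.16) = 0.385; s1 = sqrt(0.250 + 0.148) = 0.631; r = 0.250/0.398 = 0.627.
- Independent baseline: Φ(−0.288/0.545) = Φ(−0.528) = 29.9%.
- Qualifying value as baseline: 42.1%, an excess of 12.2 points, or 0.122 × 36 = 4.4 patients.
- Check by hand: the mean qualifying log value is 0.631 × 0.798 = 0.503. The expected later value is 0.627 × 0.503 = 0.316. The drop of 0.188 on the log scale is an apparent 17% fall in the geometric mean.

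**Across settings (sb 0.5 / 0.8):**

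| CV | Pool median | Independent baseline | Qualifying value as baseline | Excess, points |
|---|---|---|---|---|
| 30% | 1.5 g | 24.4% | 28.6 / 28.3% | 4.2 / 3.8 |
| 30% | 2.0 g | 24.4% | 26.5 / 27.0% | 2.1 / 2.6 |
| 40% | 1.5 g | 29.9% | 36.0 / 35.4% | 6.1 / 5.5 |
| 40% | 2.0 g | 29.9% | 33.1 / 33.6% | 3.3 / 3.8 |
| 40% | 1.0 g | 29.9% | 42.1 / 38.5% | 12.2 / 8.6 |

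Over the whole grid the excess runs from 0.4 points (CV 20%, median 2.5 g, sb 0.5) to about 30 (CV 50%, median 0.5 g, sb 0.5). The spurious mean fall at CV 40% and median 1.0 g is 0.14 to 0.20 g, against 0.00 g with an independent baseline.

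**Other readings of who qualifies.** If an earlier chart value also had to reach 1 g, the excess is 0.2 to 21 points over the grid, and 5 to 8 at CV 40% and median 1.0 g. If only the earlier value qualified the patient, it is zero.

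**Historical comparison (CV 40%, median 1.0 g, no drug effect).** With the same rule on both sides the difference is 0 points. With the qualifying value in the trial and a later value in controls it is +8 to +12 points; the odds ratio is 1.45 to 1.70 crude and still 1.36 to 1.42 after adjustment for log baseline. Moving only the trial to Day 1 gives −9 to −12 points. These mismatches are hypothetical; the plan describes none of them.

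**The case against.** The strongest reply is that the premise is not written down. UPCR is marked as standard of care, a biopsy must already exist, and conversion follows staining, so patients may be identified from earlier chart values. The Screening sample would then be a second reading, and the effect shrinks or vanishes. "Figure 3. Study Design. Protocol and outcomes measures are detailed" is a caption whose figure is not reproduced in the available text, and it may name the baseline. This stands, and is why the point is conditional.

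Second, the large figures need a pool centred at or below the cut-off. At a median of 1.0 g half of those screened fail, and the 30-point corner admits only about 16%. For patients already referred with proteinuria, 2 to 6 points is more plausible, below the binomial standard error at n = 36 of sqrt(0.3 × 0.7/36) = 7.6 points. This stands too, although a systematic shift does not average out as sampling error does.

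Third, this is a Phase I study sized on feasibility, with no response threshold to pass. Single-sample noise alone yields 15% to 33% apparent responders, more than selection adds in most settings. Both are true. The percentage is nevertheless the primary result, and selection bias is the part that is cheap to remove.

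Fourth, disease progression might offset the effect, since the Background describes worsening proteinuria. With a true rise of 10% to 30% the excess at CV 40% and median 1.0 g is still 6 to 11 points.

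A reader might also infer that the baseline is up to 60 days old, from the Day 1 column head. The documents do not establish this. The head is a table fragment, and the pregnancy test, due within 24 hours of dosing under section 7.3, is likewise ticked only at Screening, so that column may include procedures done at conversion.

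**Conclusion.** The point holds in conditional form. The Schedule offers one pre-treatment UPCR, entry rests on an unconfirmed spot value, and the visible text names no baseline. Followed most naturally, the plan uses the qualifying value as baseline, and the response percentage and mean reduction in each group are then too high.

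The size rests wholly on assumed variability and pool median: 0.4 to 30 points overall; about 2 to 6 points (1 to 2 of 36 patients) at medians of 1.5 to 2.0 g and CV 30% to 40%; 9 to 12 points at median 1.0 g and CV 40%; less if an earlier value also had to reach 1 g; zero if only an earlier value qualified the patient.

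Two stronger conclusions are tempting and not supported. One is that the Fisher test of B7-1 positive against negative is invalid: both groups pass the same filter, so the bias largely cancels unless they sit at different distances from the cut-off. The other is that the historical comparison is biased: it is unbiased if both sides use one rule, and the plan simply does not say. This is a worthwhile, inexpensive improvement and not a defect that undoes the trial.

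**What to change.** 1. For patients not yet converted, add a spot UPCR on Day 1 before the infusion, define it as the primary baseline, and use the Screening value for eligibility only. Do not average the two: with sw 0.3, sb 0.6 and median 1.0 g, the response with no true change is 33.0% on Screening, 28.0% on the average and 24.9% on Day 1.
2. For patients already converted, keep the Screening baseline, report that result separately and label it as subject to regression to the mean. Add a sensitivity analysis, where the data exist, using a pre-conversion chart UPCR not used for eligibility and chosen by a pre-stated rule, such as the one closest to Day 1. This version is dated July 2019, the first visit was planned for March 2015 and actual accrual is not stated, so this group may be most of the trial.
3. State which UPCR decides eligibility, and apply the same index, baseline and follow-up rule to historical controls. Where trial patients are split by baseline definition, match the control rule to each part.

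**Cost.** One extra spot urine at a visit already attended, some chart abstraction and a few sentences. Some Day 1 values will fall below 1 g and must stay in the analysis: 20% to 28% (7 to 10 of 36) at CV 40% and median 1.0 g, 2% to 59% over the grid. The response percentage will be somewhat lower. Some controls and converted patients will lack a second value, and 36 patients may be divided between two baseline definitions. Single-sample noise remains.
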